## INTRODUCTION

Allogeneic stem cell transplantation (HSCT) represents a fundamental therapeutic option for patients affected by malignant hematological diseases. One of the major life-threatening complication after HSCT is acute graft versus host disease (aGvHD), especially when gastrointestinal tract is extensively involved. All grade aGvHD occurred in 40-80% of HSCT recipients, depending on donor choice, stem cell source, conditioning regimen and GvHD prophylaxis. Among patients with aGvHD, intestinal involvement accounts for 60% of the cases (1). Approximately one third of patients with intestinal aGvHD reached a grade III-IV stage with an increased risk of mortality and morbidities. The most common symptom of GI involvement of acute GVHD is diarrhea, secretory and usually voluminous, often reaching more than 1.5 liters per day. In severe cases, patients presented abdominal pain and gastrointestinal bleeding may occur, reflecting the mucosal ulceration (2). These symptoms are nonspecific given the fact they might be frequently observed after allo-SCT in *Clostridium difficile* colitis, bacterial colonization, cytomegalovirus or adenovirus infection, drug toxicity, or neutropenic enterocolitis (3). Weber et al (4) reported the use of contrast enhancement ultrasound imaging (CEUS) in diagnosing gastrointestinal aGvHD. The penetration of intravenous injected contrast microbubbles into the gut lumen showed a sensitivity of 92.9% and specificity of 94.4% for intestinal aGvHD diagnosis, but the specificity was only of 39.6% for advanced stage. On the other hand, sonographic criteria

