### *Variables and Procedures*

Within 24-48 hours from symptoms, onset full panel of stool cultures will be performed together with Clostridium toxin assessment. Multiparametric ultrasound study will be performed at the onset of the symptoms and then weekly to monitoring intestinal changes accordingly to symptoms evolution during treatment. In the case with high suspicion for aGvHD (stool culture negative, persistent or progressive diarrhea, ultrasound imaging closely suggestive for aGvHD), as per common clinical practice, colonoscopy will be required to evaluate internal macroscopy features of the bowel and to obtain histological samples for conclusive diagnosis. In the meantime steroid therapy will be started, as per common clinical practice. The only modification of this protocol to common clinical practice is represented by the addition of a non-invasive bed-side method of evaluation of the patients with diarrhea. None of the routinely performed diagnostic and therapeutic process will be modified.

All patients submitted to autologous stem cell transplant who developed diarrhea between transplant date and engraftment achievement will constitute control population. Also in this case full panel of stool culture and clostridium toxin assessment will be performed at the onset of the symptoms. Multiparametric ultrasound study will be made at symptoms onset and then weekly until symptom resolution.

Multiparametric ultrasound study will be performed by expert qualified staff as following:

The examinations will be performed at patient's bed, in supine position, with a MyLab™9 Platform (Esaote, Italy) system. Fasting is required.

US for bowel requires both low-frequency convex probes (3.3-5 MHz) and high-frequency (5–17 MHz) linear assay probes to increase the spatial resolution of the intestinal wall and to assess the wall diameter and wall layer.

The following ultrasound parameters will be collected:

- Intestinal wall thickening (normal values < 3 mm; a mean of two measurements for section will be taken, in longitudinal and transverse sections).
- Intestinal wall stratification;
- Intestinal wall flow at colorDoppler;
- Strictures;
- Free fluid (FF) within the peritoneal cavity;
- Enlarged mesenteric lymph nodes;
- Mesenteric hypertrophy.

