## ENDPOINTS

### *Primary endpoint*

Primary endpoint of the study is to evaluate the accuracy of bed-side multiparametric ultrasound study in the diagnosis of gastrointestinal aGvHD in patients underwent to allogenic transplant in terms of sensitivity, specificity, positive predictive value (PPV) and negative predictive value (NPV).

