### *Statistical Analysis*

All variables included in the study will be first analyzed by descriptive statistic techniques. In depth, qualitative variables will be described as absolute and relative percentage frequencies. The Shapiro Wilk's test will be used to assess the distribution of quantitative variables. Data will be then expressed either as mean and standard deviation (SD), whether normally distributed, or as median and interquartile range (IQR), otherwise.

Between groups differences (allogenic vs. autologous transplant) will be assessed by the Fisher exact test and the Chi-square test, with Yates correction, as appropriate, in the case of qualitative variables. Quantitative data, indeed, will be assessed either by the Student's t test or the non-parametric Mann Whitney U test, as appropriate.

Receiver Operating Curve (ROC) analysis will be used to assess the accuracy of multiparametric bedside ultrasound in aGvHD diagnosis as compared to the histologic diagnosis (gold-standard, used as reference). Positive (PPV) and Negative predictive values (NPV), sensitivity and specificity will be computed, as well as the area under the ROC curve (AUROC).

To assess potential associations between bed-side multiparametric ultrasound measurements and aGvHD diagnosis in patients underwent to allogenic transplant uni- and multivariable logistic regression models will be used.

Logistic regression models will be also applied to assess whether bed-side multiparametric ultrasound (US) measurements differ in distinguishing complications different from aGvHD (i.e., infectious, drug-related or neutropenic colitis) in patients underwent to allogenic transplant as compared to auto-transplant. More in depth, to evaluate the combined effects between US measurements and transplant group, multivariable interaction models will be fitted, and the interaction odd ratios (IOR) evaluated. In particular, for each US measurement, one interaction logistic regression model will be fitted. In summary, the coefficients of the main effects (in exponential terms) will be interpreted as ORs of the outcome by considering the allo-transplant group from control ( $OR_{\text{autologous}}$ ), by

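### The study ultrasound is listed among the triggers for the biopsy that serves as its own reference standard, although the protocol says routine care is unchanged

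*Combined protocol and SAP*

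**What the plan says.** The conflict lies within one paragraph of Variables and Procedures.

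- **Status of the ultrasound.** "The only modification of this protocol to common clinical practice is represented by the addition of a non-invasive bed-side method of evaluation" of patients with diarrhea. The paragraph then closes: "None of the routinely performed diagnostic and therapeutic process will be modified".
- **Trigger.** High suspicion of aGvHD is explained in parentheses as "stool culture negative, persistent or progressive diarrhea, ultrasound imaging closely suggestive for aGvHD". No 'and', 'or' or 'only if' joins the three items.
- **What the trigger leads to.** In that case "colonoscopy will be required to evaluate internal macroscopy features of the bowel and to obtain histological samples for conclusive diagnosis". On treatment: "In the meantime steroid therapy will be started, as per common clinical practice". The colonoscopy, like the steroids, is described as usual practice.
- **Timing.** The scan is done when symptoms begin and repeated weekly.

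Two other sections make this matter for the analysis. The primary endpoint is accuracy in allogeneic patients, "in terms of sensitivity, specificity, positive predictive value (PPV) and negative predictive value (NPV"). Statistical Analysis has the ultrasound assessed "as compared to the histologic diagnosis (gold-standard, used as reference").

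The available text does not provide for histology independent of the scan, a reference diagnosis for patients without biopsy, or an adjustment for partial verification.

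**The concern.** A test that the protocol adds to practice cannot also be part of a routine trigger that the protocol leaves unchanged. One of the two statements has to give way, and the text does not say which.

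The first consequence is for the primary endpoint. Colonoscopy supplies the histology, and the index test is named among the features that lead to colonoscopy. If patients with a suggestive scan are biopsied more often, false negatives and true negatives are under-represented among verified patients. Apparent sensitivity then rises and apparent specificity falls. This is partial verification bias, and enrolling more patients does not reduce it.

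The second consequence is for care. Take a patient with negative stool cultures, persisting diarrhea and a non-suggestive scan. The trigger, read literally, leaves this patient out; the closing sentence of the paragraph keeps the patient on the routine pathway. The Introduction makes scan-influenced treatment foreseeable, because it presents ultrasound as a way to start steroids more safely than on clinical suspicion alone.

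**Working it through.** **Plan's own figure.** There is none to reproduce. The sample size section makes no formal calculation, and nothing states how often patients with a non-suggestive scan would be biopsied.

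**Inputs, all assumed.**
- k = histology rate after a non-suggestive scan divided by the rate after a suggestive scan. k = 1 means verification does not depend on the scan.
- True sensitivity (Se) and specificity (Sp) of 80% each.
- As a second case, the Introduction's report that a contrast-ultrasound sign "showed a sensitivity of 92.9% and specificity of 94.4% for intestinal aGvHD diagnosis". That sign is microbubble penetration into the gut lumen. It is not among the parameters this study lists, so the values are borrowed only to show a high-accuracy case.
- Selection depends on the scan alone.

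**Formulas.** Among verified patients:
- apparent Se = Se / (Se + (1 − Se) × k)
- apparent Sp = Sp × k / (Sp × k + (1 − Sp))

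Prevalence cancels from both.

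**Se = Sp = 80%.**
- k = 0.5: Se = 0.80 / (0.80 + 0.20 × 0.5) = 0.80 / 0.90 = 88.9%; Sp = 0.40 / (0.40 + 0.20) = 66.7%.
- k = 0.25: Se = 0.80 / (0.80 + 0.05) = 94.1%; Sp = 0.20 / (0.20 + 0.20) = 50.0%.

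**Se = 92.9%, Sp = 94.4%.**
- k = 0.5: Se = 0.929 / (0.929 + 0.0355) = 96.3%; Sp = 0.472 / (0.472 + 0.056) = 89.4%.
- k = 0.25: Se = 0.929 / (0.929 + 0.01775) = 98.1%; Sp = 0.236 / (0.236 + 0.056) = 80.8%.

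**Predictive values.** With selection on the scan alone and k above 0, PPV and NPV are unbiased, because k multiplies both cells of the scan-negative row and cancels. If the few scan-negative patients biopsied are chosen for strong clinical suspicion, NPV describes that selected group.

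**Limiting case.** At k = 0 the formulas give 100% and 0%, and NPV has no denominator. This needs two further conditions: the clinician's impression of a suggestive scan is the same as the positive or negative call analysed, and no scan-negative patient is biopsied, including after a later weekly scan.

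**Relaxing the first condition.** Suppose only patients whose scan impression is suggestive are biopsied, but the analysed marker is a different reading. Let impression and marker each have 80% sensitivity and specificity and be bivariate normal within disease status (assumption). Apparent sensitivity and specificity are then 85.9% and 56.4% at correlation 0.5, and 91.1% and 35.5% at correlation 0.8. The direction is unchanged, and the extreme values disappear.

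**The case against.** The strongest defence is that the parenthesis only illustrates what high suspicion looks like. It contains no connective that makes it a rule, it is tied to usual practice, and the closing sentence says routine care is not modified. On that reading, a culture-negative patient with persisting diarrhea gets the same work-up whatever the scan shows. This is a fair reading, and it is why a strict gate cannot be asserted. It does not remove the conflict: the list still names the scan, and nowhere is it stated that care proceeds regardless of its result. Any dependence of biopsy on the scan (k below 1) is enough for bias.

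Secondly, the adverse events section describes SonoVue imaging as established in gastrointestinal diagnostics, so ultrasound might already be routine. But that concerns contrast imaging in general, while Variables and Procedures treats this bed-side method as the protocol's one change to practice.

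Thirdly, a reader might infer that the design must yield 100% sensitivity, 0% specificity and no NPV. The documents do not support that. They define no single positive or negative call: many separate measurements are collected and a ROC analysis is planned, so a biopsied patient can fall below an analysed cut-off. Weekly scans also allow a patient with a non-suggestive first scan to reach biopsy later.

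Finally, k is not derivable from the documents, and a wording change may not fully control it. Both points stand.

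**Conclusion.** The concern holds in a limited form. The paragraph contradicts itself, and to the extent its trigger is followed, receipt of the histologic reference depends on the test under evaluation. The direction of bias on the primary endpoint is clear: sensitivity up, specificity down. Specificity suffers more in the illustrations, losing 13.3 and 30.0 percentage points in the 80% case (80.0 − 66.7 and 80.0 − 50.0), against gains in sensitivity of 8.9 and 14.1 points.

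These sizes rest on assumed k, assumed true accuracy, and selection on the scan alone. They show what is possible and do not forecast this trial. Calling the study a pilot does not answer the point, because the bias does not depend on sample size. Since the likely size is unknown and the correction is cheap, this should be changed, but it does not show that the study cannot estimate accuracy.

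**What to change.** Make two wording changes in Variables and Procedures.

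1. Define high suspicion by routine features only: negative stool cultures, diarrhea that persists or worsens, and usual clinical judgement. Remove the ultrasound item from the list.
2. Add: *Colonoscopy and steroid decisions follow routine care regardless of the ultrasound result, at onset and at the weekly scans.*

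Optionally, record whether the scan contributed to each colonoscopy decision, so that any remaining dependence can be described. Withholding scan results from the treating team would protect further, but that is a trade-off for the sponsor and is not required here.

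The cost is an edit to one paragraph, with no added procedure, visit or mandatory data field, and it carries out the sponsor's stated intent. The downside is that wording does not stop clinicians who see the scan from acting on it, so some scan-dependent verification may remain. Routine colonoscopy will also still be selective on clinical features.

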## ENDPOINTS

### *Primary endpoint*

Primary endpoint of the study is to evaluate the accuracy of bed-side multiparametric ultrasound study in the diagnosis of gastrointestinal aGvHD in patients underwent to allogenic transplant in terms of sensitivity, specificity, positive predictive value (PPV) and negative predictive value (NPV).

### *Secondary endpoints*

- To assess potential associations between bed-side multiparametric ultrasound measurements weekly performed and aGvHD diagnosis in patients underwent to allogenic transplant.
- To assess whether bed-side multiparametric ultrasound measurements at baseline differ in distinguishing complications different from aGvHD (i.e., infectious, drug-related or neutropenic colitis) in patients underwent to allogenic transplant as compared to auto-transplant.

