## STATISTICAL ANALYSIS PLAN

### *Sample Size calculation*

The literature reports various experiences on the use of SWE in the study of the intestine, especially in patients with chronic inflammatory bowel diseases. But no data are reported on the use of the method in patients with graft versus host disease. Hence, we consider this as a pilot study. As such, no formal sample size calculation is needed. However, based on common rules on pilot studies [10], the minimum sample size required would be of 20 subjects. In our department, given the median annual number of allogenic stem cell transplant, we plan to enroll 75 patients. As for the secondary endpoints, an equal number of age-matched patients undergone to autologous transplant will be enrolled.

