fixing US measurements values to 0 (null), and ORs of the outcome by considering a unit increase of the US measurements in the auto-transplant group ( $OR_{US\_measurements}$ ). The interaction parameters (IOR) will be interpreted as difference (in OR terms) of the US measurements variations between transplant groups (autologous transplant as reference category).

Statistical significance will be set at P value  $< 0.05$ . P values between 0.05 and 0.10 will be further reported as suggestive. All analyses will be performed by using R software (v. 4.1.2, R Core Team, 2021) [11].

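### The first secondary endpoint relates weekly repeated scans to one aGvHD diagnosis per patient, but the SAP names only ordinary logistic regression, with no unit of analysis and no rule for scans after steroid start

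*Combined protocol and SAP*

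**What the plan says.** Secondary endpoints: the first bullet concerns "associations between bed-side multiparametric ultrasound measurements weekly performed and aGvHD diagnosis" in allogeneic patients. The second asks whether "bed-side multiparametric ultrasound measurements at baseline differ". The document therefore separates repeated from single-time data, and only the second bullet fixes a time point.

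Variables and Procedures: scans are done at symptom onset and then "weekly to monitoring intestinal changes accordingly to symptoms evolution during treatment". When suspicion is high, colonoscopy is requested "to obtain histological samples for conclusive diagnosis", which implies one diagnosis per patient. The same paragraph adds: "In the meantime steroid therapy will be started".

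Statistical Analysis: for this association, "uni- and multivariable logistic regression models will be used". That sentence does not mention the weekly schedule. The other methods serve other purposes: group tests compare allogeneic with autologous patients, ROC analysis serves the primary endpoint, and the interaction models serve the second secondary endpoint. There is no patient random effect, GEE, clustered error, per-patient summary or choice of scan. Treatment given for diarrhea is recorded (Data Collection) but enters no model.

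**The concern.** Ordinary logistic regression assumes independent rows. If each weekly scan is a row, one patient's diagnosis is repeated over correlated measurements. The standard errors are then too small, and too many ultrasound parameters appear associated with aGvHD. The plan also states that "P values between 0.05 and 0.10 will be further reported as suggestive", so the list of named parameters would lengthen further. That sentence is a reporting label, however, and has nothing to do with correlation.

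The second problem is treatment. Steroids start during the scan series, in patients in whom aGvHD is strongly suspected. The Introduction reports from earlier work that the picture normalises in complete responders. In partial responders the bowel wall looks normal on conventional ultrasound, while CEUS still detects microvascular change. Later scans therefore mix diagnosis with response. This dilutes the association, and the dilution should be weaker for CEUS parameters. It acts against the inflation of significance, so a pooled result could not be corrected by eye.

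Because the unit of analysis is not fixed, the choice could be made after the data are seen.

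**Working it through.** **Inputs from the documents.** 75 allogeneic patients ("we plan to enroll 75 patients"); significance at P<0.05, taken as two-sided. The 75 rests on transplant volume and the pilot minimum of 20 on a general rule, so there is no sample size formula to reproduce.

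**Assumptions.** Scans per patient m = 2 to 6; ICC of a measurement within patient 0.3 to 0.7; 38 cases of 75 unless stated. None of these is in the documents.

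**1. Type I error if scans are pooled as independent rows.** Diagnosis is constant within patient, so the variance is understated by the design effect DE = 1 + (m − 1) × ICC. The actual error is 2 × [1 − Φ(1.96/√DE)]. Example with m = 4 and ICC 0.5: DE = 2.5, 1.96/√2.5 = 1.24, error 21.5%. The 75 × 4 = 300 rows carry the information of 300/2.5 = 120.

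| Scans | ICC 0.3 | ICC 0.5 | ICC 0.7 |
|---|---|---|---|
| 2 | 8.6% | 11.0% | 13.3% |
| 3 | 12.1% | 16.6% | 20.6% |
| 4 | 15.5% | 21.5% | 26.6% |
| 6 | 21.5% | 29.5% | 35.6% |

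Simulated pooled logistic regression agrees: 8.4-13.3% with 2 scans, 14.8-27.2% with 4, 21.0-34.0% with 6. With unequal scan numbers (1 to 6, unrelated to diagnosis; 15, 38 or 55 cases) it gave 16.8-30.6%. With patient-clustered errors it was 4.3-7.2%, and with one scan per patient 3.6-5.2%.

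**2. Dilution after steroid start.** For a measurement shifted in cases, the pooled log odds ratio per SD is roughly the mean shift over the scans. Take 4 scans and an onset shift of 0.5 SD:

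- No fading: mean 0.5, odds ratio e^0.5 = 1.65 (simulated 1.66).
- Linear halving by the fourth scan: mean (0.5 + 0.25)/2 = 0.375, odds ratio e^0.375 = 1.45 (simulated 1.45).
- Linear fading to zero: mean 0.25, odds ratio e^0.25 = 1.28 (simulated 1.28).

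**3. Do the weekly scans add power for the diagnostic question?** Same setting, ICC 0.5. For the mean of 4 scans, the standard error of the group difference is √[(2.5/4) × (1/38 + 1/37)] = 0.183. For the onset scan alone it is √(1/38 + 1/37) = 0.231. Power is approximately Φ(shift/SE − 1.96).

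| Course of the 0.5 SD shift | Weekly, by formula | Weekly clustered, simulated | Onset scan, simulated |
|---|---|---|---|
| No fading | 78% | 76-79% | 56-58% |
| Halves | 54% | 54% | 55% |
| Fades to zero | 28% | 25-27% | 55-56% |

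The formula gives 58% for the onset scan in every row. The weekly scans help only if the difference does not fade.

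**The case against.** The strongest reply is that no section says scans will be pooled. A reader might infer from the first endpoint and the named model that pooling is planned and that its P values will be inflated. The documents do not support that. One row per patient is an ordinary reading. A separate logistic model for each week also fits the text, uses the weekly data and has no correlated rows, at the price of multiplicity over weeks. This stands: the inflation figures are conditional on one of several readings, and their upper end needs 6 scans with ICC 0.7. What remains is that the plan does not choose among readings that give different answers, and that a model per week still leaves steroid exposure in the later weeks unaddressed.

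A reader might also infer that a correct repeated-measures model would generally gain power from the weekly scans. The third calculation shows that it would not, and the Introduction's own account of response makes fading likely for conventional ultrasound. For CEUS in partial responders, complete fading is not to be expected.

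Nor can it be taken as fact that scan numbers follow symptoms in allogeneic patients. The text says that monitoring accords with how symptoms evolve; an explicit stop at resolution is given only for the autologous controls. Scan numbers may therefore differ by diagnosis, but this is not certain.

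Finally, this is an exploratory endpoint of a declared pilot. That lowers the stakes and excuses the missing power calculation, but it does not settle what a row is.

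**Conclusion.** The point holds as a gap with a conditional consequence. The first secondary endpoint is built on weekly scans. The only model named for it does not define its unit of analysis, allow for within-patient correlation or deal with scans after steroid start. If scans were pooled as independent rows, type I error at P<0.05 would be about 9-13% with 2 scans and 12-36% with 3-6, for an assumed ICC of 0.3-0.7. In the same analysis, fading after steroid start could reduce an onset odds ratio of about 1.7 per SD to between 1.3 and 1.5. All of these sizes rest on assumed scan counts, ICC, case numbers and fading patterns.

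The second secondary endpoint is limited to baseline and is not affected. This is a change that should be made, but it is not critical to the study.

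**What to change.** State in the SAP that weekly scans will not be analysed as independent rows, and then:

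1. Fit the diagnostic logistic models with one row per patient, using the symptom-onset scan. Flag that scan if it was taken after steroid start.
2. Analyse the weekly series separately, with each ultrasound parameter as outcome and a link suited to its type. Use a mixed model with a patient random effect, or GEE with patient-clustered errors and a small-sample correction. Include aGvHD, week, their interaction and a time-varying indicator of steroid exposure. Read the result as describing the course under treatment, not diagnostic accuracy.
3. Report scans per patient by diagnosis.

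The endpoint wording can stay, and no scan or treatment changes. The cost is SAP text, standard R packages and the steroid start date, which must be captured within the treatment data already collected. There are more models to fit: about 16 parameters (7 conventional, 8 time-intensity, plus elastography). Intervals will be wider than under naive pooling. Because steroids follow suspicion of aGvHD, the steroid and aGvHD terms will overlap and be estimated imprecisely.

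GEE can be liberal with few cases or few non-cases. In a null simulation (15, 38 or 55 cases of 75, ICC 0.5), the joint 2-df test rejected 6.5-10.8% uncorrected and 4.8-8.6% with the Mancl-DeRouen correction. A random-intercept model, whose structure matched the simulation, gave 4.6-6.8%. Those checks used a linear model without the steroid term; binary and ordinal links were not tested. The change does not address multiplicity over the parameters.
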